6.5 Visit 4 (3 Month Follow-Up)

Subjects will return 90 +/- 7 days after PAE to complete IPSS, IIEF, and QOL questionnaires; to have Qmax and PVR measured; and to have a follow up CT of the pelvis to evaluate for non-target embolization and PV changes as well as percent prostate infarction.

[figure not shown]
6.6 Visit 5 (6 Month Follow-Up)

Subjects will return 180 +/- 7 days after PAE to complete IPSS, IIEF, and QOL questionnaires and to have Qmax and PVR measured.

6.7 Visit 6 (12 Month Follow-Up)

Subjects will return 360 days +/- 14 days after PAE to complete IPSS, IIEF, and QOL questionnaires and to have Qmax and PVR measured.

6.8 Study Procedure Flow Chart

7.0 Safety and Effectiveness Assessments

7.1 Safety Assessments

Subjects will be observed for several hours after PAE to monitor for immediate complications to include bleeding, infection and acute ischemia of the rectum and bladder. Subjects will be contacted by study personnel the day after PAE to inquire about delayed onset complications. The subjects will also be given a phone number that they can call to reach a nurse if they believe they have developed a complication of the procedure.

7.2 Effectiveness Assessments

Technical success will be defined as bilateral prostatic artery embolization. This will be determined during the procedure. Clinical success will be defined by a reduction of IPSS of $\geq 25\%$ and reduction of QoL by ≥ 2 . The size of the prostate will be measured by CT at 3 the follow-up visit. IPSS, QoL, IIEF, PVR and Qmax will be measured at 3, 6 and 12-month follow-ups.

8.0 Statistical Plan

8.1 Sample Size Determination

Twenty subjects will be enrolled into this pilot study. Because there is no previous study reporting results for PAE with LC Bead LUMI, this pilot study will provide sample size data for a larger trial with adequate power. Due to budgetary constraints, we have selected a sample size of 20 participants. Given our sample size, and using parameters determined from prior studies, we expect to have 3.60% precision for the estimate of percent change in IPSS score from baseline to 6 month follow-up.(1)

8.2 Statistical Methods

Fractions and percentages will be used to describe technical and clinical success rates as well as major, minor and specific complication rates. Descriptive statistics including means and standard deviations will be used to summarize both discrete questionnaire scores and continuous values for prostate size, Qmax, and PVR for the 3-12 month follow-up period. Prostate size is only measured before the procedure and 3 months after the procedure. Percent change will be calculated between the baseline and final values. Continuous measures will be described using 95% confidence intervals. Feasibility for a future trial will be assessed using retention rates at each visit. Retention rates will be used to plan sample sizes for future studies.

Any deviations from the previously described statistical plan will be described and justified in a protocol amendment and/or in the final report submitted to the IDE application.

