3.3 Secondary Study Endpoints

1. Improvement of QoL score at 6 months
2. Improvement of uroflowmetry (Qmax, PVR) at 6 months
3. Reduction of prostate volume at 6 months
4. Percentage of prostate infarcted at 6 months
5. Incidence of non-target embolization at 6 months
6. Incidence of minor complications at 6 months
7. Improvement in IIEF at 6 months

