4.3 Inclusion Criteria

1. Male
2. Age > 40
3. Prostate gland >50 grams as measured by pre-procedural CT
4. Have previously taken BPH medication for 6 months without desired improvement of LUTS or has started medication and stopped due to unwanted side effects
5. Moderate to severe LUTS as defined by IPSS score >18
6. Peak urine flow rate (Qmax) <12 ml/sec
7. Capable of giving informed consent
8. Life expectancy greater than 1 year

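### Percent change, the only change measure in section 8.2, is unsuitable for PVR, whose baseline can be zero or near zero

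*Combined protocol and SAP*

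**What the plan says.** Section 8.2 plans means and standard deviations to "summarize both discrete questionnaire scores and continuous values for prostate size, Qmax, and PVR for the 3-12 month follow-up period". It then notes that "Prostate size is only measured before the procedure and 3 months after the procedure", and continues: "Percent change will be calculated between the baseline and final values". Interval estimates follow: "Continuous measures will be described using 95% confidence intervals". Section 8.2 plans no absolute change from baseline. It does not say whether percentages are computed for each man and averaged or computed between group means, and it has no rule for a zero baseline.

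PVR change is within the study's aims. Section 2.0 lists it among the quantities whose distribution the pilot is meant to estimate, and section 3.3 lists "Improvement of uroflowmetry (Qmax, PVR) at 6 months" as a secondary endpoint. Section 7.2 confirms the data: "IPSS, QoL, IIEF, PVR and Qmax will be measured at 3, 6 and 12-month follow-ups".

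The entry criteria in section 4.3 require IPSS above 18 and a prostate above 50 g. Qmax has an upper limit only: "Peak urine flow rate (Qmax) <12 ml/sec". Neither section 4.3 nor section 4.4 sets a minimum PVR; complete urinary retention is excluded, which removes men at the other extreme. Section 8.3 says that every subject's data enter the analysis.

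**The concern.** A percent change divides by the baseline value. That is safe when eligibility keeps the baseline well above zero, as it does for IPSS and prostate size. It is unsafe for PVR, because a man who empties his bladder well can enter with little or no residual. At 0 ml his percent change does not exist, and section 8.3 cannot then be followed on that scale. At a few ml, a clinically small rise becomes a percentage in the hundreds and can outweigh several men whose residual halved.

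At stake are the PVR estimate and its spread. Section 8.1 says the pilot is to supply sample-size data for a larger trial. The planned means and SDs of PVR at follow-up do not fill the gap, because the SD of within-man change cannot be recovered from them.

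**Working it through.** **Plan's own figure.** The documents give no expected PVR, no PVR variance and no precision for PVR, so there is no figure to reproduce. The one stated precision, 3.60% in section 8.1, concerns IPSS. It comes without an SD or confidence level, and nothing below depends on it.

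**Inputs from the documents.** n = 20 (section 8.1: "Due to budgetary constraints, we have selected a sample size of 20 participants"); IPSS above 18 and prostate above 50 g at entry (section 4.3); no lower PVR limit (sections 4.3 and 4.4). Every PVR value below is an assumption.

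**1. Zero baselines.** If a proportion p of eligible men have a PVR of 0 ml, the chance of at least one among 20 is 1 - (1 - p)^20.

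| Assumed p | Chance of at least one undefined percentage |
|---|---|
| 1% | 18% |
| 2% | 33% |
| 5% | 64% |
| 10% | 88% |

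**2. A four-man illustration.** Baseline 200, 150, 100 and 10 ml; follow-up 100, 75, 50 and 60 ml.

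- Absolute changes: -100, -75, -50, +50. Mean = -175/4 = -43.75 ml.
- Individual percent changes: -50, -50, -50, +500. Mean = 350/4 = +87.5%.
- Group means: 460/4 = 115 ml and 285/4 = 71.25 ml. Change = 71.25/115 - 1 = -38%.

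The same data give a fall on two scales and a large rise on the third. The wording of section 8.2 permits either percentage.

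**3. Size at n = 20.** Model: each man has a true log-normal PVR (median 70 ml). The true value falls by 40%. Baseline and follow-up each carry independent log-normal noise with log SD s. Each man's ratio of follow-up to baseline then has expectation 0.6 × exp(s²), so the expected mean percent change is 0.6 × exp(s²) - 1. The between-man spread cancels from the ratio, so s drives the result. The table gives 20,000 simulated trials per setting; the ranges for absolute change are for between-man log SD 0.8 and 1.2.

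| s (assumed) | Expected mean percent change | Wrong sign, mean percent change | Wrong sign, mean absolute change |
|---|---|---|---|
| 0.3 | -34% | 0% | 0.0% to 0.2% |
| 0.4 | -30% | 0.5% | 0.2% to 1% |
| 0.5 | -23% | 6% | 1% to 3% |
| 0.6 | -14% | 21% | 3% to 6% |
| 0.7 | -2% | 40% | 5% to 8% |

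Check at s = 0.6: 0.6 × exp(0.36) - 1 = 0.6 × 1.433 - 1 = -0.14. The upward bias is present in every row, since the true fall is 40%. The sign problem is negligible at s = 0.3 and serious at 0.6 and above.

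**4. The other measures.** IPSS: the baseline is at least 19, so the percentage is always defined. A deliberately unfavourable example (16 men from 35 to 25, 4 men from 19 to 35) keeps its sign: -4.8 points and -6.0%. QoL: with an assumed 0 to 6 range and assumed baselines, the sign reversed in 0% of simulated trials in which the mean score fell when the mean shift was 2 points, and in 1% to 5% when it was 0.5 points.

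**The case against.** The strongest reply is that the percent-change sentence names no measure and directly follows one about prostate size alone. The only other relative measures of change, the IPSS precision in section 8.1 and the IPSS success rule of at least 25% in section 7.2, concern IPSS. On that reading, percent change may be meant only where it is sound. This stands as a point about wording: a reader might infer that section 8.2 prescribes percent change for every measure, and the text does not say so. It does not remove the gap, because on the narrow reading section 8.2 has no change measure for PVR at all, although section 2.0 asks for one.

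Second, averaging individual percentages is only one reading. The change in group means is defined even when some men start at zero, and it has the right sign in the illustration. This stands, and the sign reversal is therefore conditional on the averaging reading.

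Third, a reader might extend the criticism to QoL, IIEF and Qmax. The documents do not support that. They give no score range for QoL or IIEF, section 7.2 already judges QoL success in points (a reduction of at least 2), reversal for QoL was rare in simulation, and no case against percent change for Qmax has been shown.

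Fourth, a reader might take a single wrong-sign rate, such as 21%, as the size of the problem. That figure belongs to one assumed within-man SD, and no document figure supports that value over others.

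Finally, raw PVR is collected at each visit, so absolute change can be computed later, and section 8.2 allows justified deviations. That limits the harm, but a pre-stated measure is preferable and costs almost nothing.

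**Conclusion.** The concern holds for PVR. Section 8.2 offers percent change as its only change measure, without stating its scope, and eligibility allows PVR baselines at which an individual percentage is undefined or extreme. That much follows from the documents alone. The size does not. With a true 40% fall and 20 men, the mean of individual percentages has the wrong sign in 0% to about 40% of trials as the within-man log SD goes from 0.3 to 0.7, under a log-normal model with independent noise at the two visits. These are assumptions, and the result applies only if individual percentages are averaged.

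The primary endpoint, IPSS, and prostate size are not affected. Severity is minor: PVR is part of one secondary endpoint in a single-arm, descriptive pilot.

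**What to change.** In section 8.2, state that percent change applies to IPSS and prostate volume. For PVR, report absolute change from baseline in ml with a 95% confidence interval, together with the median and interquartile range because the distribution is likely to be skewed. Absolute change is defined at a zero baseline, so section 8.3 can then be followed for every man with both measurements. Report QoL change in points, to match the success rule in section 7.2.

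The cost is a sentence or two in section 8.2. No extra visit, measurement or data item is needed.

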8.3 Subject Population(s) for Analysis

All subjects' data will be included for analysis even if follow up data is incomplete. Every attempt will be made to ensure that there is as little missing data as possible including reminder phone calls and follow-up phone calls if a subject misses a visit.

8.4 Interim Analysis

No interim analysis is planned.

9.0 Risk Analysis

9.1 Anticipated Risks

A recent meta-analysis of PAE data from 662 patients in nine studies reported only two major complication (0.3% major complication rate) involving bladder ischemia requiring surgery and severe urinary sepsis requiring hospitalization. Among minor complications transient rectalgia and/or dysuria (9.1%), acute urinary retention (7.9%) and transient hematuria (4.4%) were the most common (1).

9.2 Adverse Event Definitions

Adverse events, Serious Adverse Events and Product Malfunctions

An adverse event (AE) is defined as any untoward or unfavourable medical occurrence in a human patient or clinical trial subject administered a medicinal product, including any abnormal sign (for example, abnormal physical exam or laboratory finding), symptom, or disease, temporally associated with the patient's participation in the research, and which does not necessarily have a causal relationship with this treatment (study medication, application of the study device, etc.) or study participation. It includes all adverse events regardless of seriousness or relatedness.

A serious adverse event (SAE) is defined as an adverse event that

- a) Results in death
- b) Led to a serious deterioration in health that either:
 - I. Results in a life-threatening illness or injury, or
 - II. Results in a permanent impairment of a body structure or a body function,
or
 - III. Requires in-patient hospitalization or prolongation of existing hospitalization, or
 - IV. Results in medical or surgical intervention to prevent life threatening illness or injury or permanent impairment to a body structure or a body function.
 - V. Results in a persistent or significant disability/incapacity or substantial disruption of the ability to conduct normal life functions.
- c) Led to fetal distress, foetal death or a congenital abnormality or birth defect

A product malfunction is defined as a failure of the device to meet its performance specifications, essential function or otherwise perform as intended. Performance specifications include all claims made in the labelling for the device. The essential function of a device refers not only to the device's labelled use, but for any use widely prescribed within the practice of medicine.

Reporting of Adverse Events, Serious Adverse Events and Device Malfunctions

The Institution and/or the Sponsor-Investigator shall report all and any serious adverse events, product malfunctions or quality complaints (regardless of causality) that they become aware of in relation to the Product and/or the investigation to BTG.

All reports will be exchanged in English and Sponsor-Investigator will also provide BTG with such information and reasonable assistance as may be requested by BTG to allow BTG to comply with their obligations.

The Institution and/or the Sponsor-Investigator shall report all SAEs and incidents impacting patient safety to [contact].

SAEs

The Sponsor-Investigator will report SAEs within **one business day** to enable BTG to comply with their obligations as the device manufacturer, under applicable laws and regulations.

All reports will contain the following, if available:

- Study title and name of the Sponsor-Investigator.
- Patient number
- Adverse event number
- Date of event occurrence/date notified
- Product details
 - Product name/ part number
 - Size / dose
 - Batch / lot number
- Adverse event details along with comprehensive event description
- Action(s) taken to treat or resolve the event
- Outcome
- Investigators opinion of causality of event i.e. related to
 - Drug
 - Device
 - Procedure
- Product returned to BTG if applicable

Device Malfunctions

The Institution and/or the Sponsor-Investigator shall report all device malfunctions and/or quality complaints to within one business day of becoming aware of the issue.

9.3 Recording of Adverse Events

Research subjects will be questioned about adverse effects by telephone the day following the procedure. In addition they will be given a pager number to reach a physician 24 hours a day to report adverse effects and receive medical advice. The subjects will also be questioned about possible adverse effects at each follow-up visit.

All observed or volunteered adverse effects (serious or non-serious) and abnormal test findings, regardless of treatment group, if applicable, or suspected causal relationship to the investigational device or, if applicable, other study treatment or diagnostic product(s) will be recorded in the subjects' case histories. For all adverse effects, sufficient information will be pursued and/or obtained so as to permit 1) an adequate determination of the outcome of the effect (i.e., whether the effect should be classified as a *serious adverse effect*) and; 2) an assessment of the casual relationship between the adverse effect and the investigational device or, if applicable, the other study treatment or diagnostic product(s).

Adverse effects or abnormal test findings felt to be associated with the investigational device or, if applicable, other study treatment or diagnostic product(s) will be followed until the effect (or its sequelae) or the abnormal test finding resolves or stabilizes at a level acceptable to the investigator-sponsor.

An abnormal test finding will be classified as an *adverse effect* if one or more of the following criteria are met:

- The test finding is accompanied by clinical symptoms

- The test finding necessitates additional diagnostic evaluation(s) or medical/surgical intervention; including significant additional concomitant drug treatment or other therapy
 - Note: simply repeating a test finding, in the absence of any of the other listed criteria, does not constitute an adverse effect.
- The test finding leads to a change in study protocol or discontinuation of subject participation in the clinical research study
- The test finding is considered an adverse effect by the Sponsor-Investigator.

9.4 Causality and severity assessment

The investigator-sponsor will promptly review documented adverse effects and abnormal test findings to determine 1) if the abnormal test finding should be classified as an adverse effect; 2) if there is a reasonable possibility that the adverse effect was caused by the investigational device or, if applicable, other study treatment or diagnostic product(s); and 3) if the adverse effect meets the criteria for a *serious adverse effect*.

If the investigator-sponsor's final determination of causality is "unknown and of questionable relationship to the investigational device or, if applicable, other study treatment or diagnostic product(s)", the adverse effect will be classified as *associated with the use of the investigational device or study treatment or diagnostic drug product(s)* for reporting purposes. If the investigator-sponsor's final determination of causality is "unknown but not related to the investigational device or, if applicable, other study treatment or diagnostic product(s)", this determination and the rationale for the determination will be documented in the respective subject's case history.

9.5 Reporting of Adverse Effects and Unanticipated Problems

9.5.1 Reporting of adverse reactions to the FDA

The investigator-sponsor will submit a completed [FDA Form 3500A](#) to the FDA's Center for Devices and Radiological Health for any observed or volunteered adverse effect that is determined to be an *unanticipated adverse device effect*. A copy of this completed form will be provided to all participating sub-investigators.

The completed [FDA Form 3500A](#) will be submitted to the FDA as soon as possible and in no event, later than 10 working days after the investigator-sponsor first receives notice of the adverse effect.

If the results of the sponsor-investigator's follow-up evaluation show that an adverse effect that was initially determined to not constitute an *unanticipated adverse device effect* does, in fact, meet the requirements for reporting; the investigator-sponsor will submit a completed [FDA Form 3500A](#) as soon as possible, but in no event later than 10 working days, after the determination was made.

For each submitted [FDA Form 3500A](#), the sponsor-investigator will identify all previously submitted reports that that addressed a similar adverse effect experience and will provide an analysis of the significance of newly reported adverse effect in light of the previous, similar report(s).

Subsequent to the initial submission of a completed [FDA Form 3500A](#), the investigator-sponsor will submit additional information concerning the reported adverse effect as requested by the FDA.

9.5.2 Reporting Adverse Events to the Responsible IRB

In accordance with applicable policies of the University of North Carolina Institutional Review Board (IRB), the investigator will report, to the IRB, any observed or volunteered adverse effect that is determined to be (1) unexpected; (2) related or possibly related to the research; and (3) involves increased or greater risk of harm to participant(s) or others than was previously known or approved by the IRB. Adverse effect reports will be submitted to the IRB in accordance with the IRB policies and procedures.

9.6 Stopping Rules

The study will be stopped if there is greater than one major complication as defined by the Society of Interventional Radiology Classification System for Complications by Outcome (7).

9.7 Medical Monitoring

9.7.1 Data and Safety Monitoring Plan

Safety Monitoring will be performed by a licensed physician who is not a study investigator. The CRFs and any relevant source documents will be sent to the medical safety monitor (as above) who will review them after treatment is complete for subject 1, 5, 10 and 20.

Complications will be assessed by the PI, categorized into major and minor categories and recorded on the CRF. CRFs and appropriate source documents will be made available to this individual for bi-monthly (every 2 months) review to ensure completeness of data collection. Any discrepancies will be immediately addressed by the PI. All adverse events will be recorded and then summarized for inclusion in the final manuscript.

Data monitoring will be performed by an individual who is not a study investigator. CRFs and appropriate source documents will be made available to this individual for bi-monthly review to ensure completeness of data collection. Any discrepancies will be immediately addressed by the PI.

9.7.2 Data and Safety Monitoring Board

Because this is a pilot study with only 20 subjects, no DSMB will be used for this study. Data and safety monitoring will be conducted by individuals who are not investigators on this study.

10.0.1 Data Handling and Record Keeping

10.1 Confidentiality

Information about study subjects will be kept confidential and managed according to the requirements of the Health Insurance Portability and Accountability Act of 1996 (HIPAA). Consistent with these regulations a signed authorization will be obtained that informs each subject of the following:

- What protected health information (PHI) will be collected from subjects in this study
- Who will have access to that information and why
- Who will use or disclose that information
- The rights of a research subject to revoke their authorization for use of their PHI.

In the event that a subject revokes authorization to collect or use PHI, the investigator, by regulation, retains the ability to use all information collected prior to the revocation of subject authorization. For subjects that have revoked authorization to collect or use PHI, attempts should be made to obtain permission to collect at least vital status (i.e. that the subject is alive) at the end of their scheduled study period.

